4.1.5 Dose Delay, Interruption, or Discontinuation

If the dose of nivolumab, daratumumab, pomalidomide and/or dexamethasone is interrupted or discontinued, the treatment with the other drugs may continue as scheduled if deemed in their

best interest by both the PI and the BMS medical monitor. Subjects must be deriving clinical benefit.

Each cycle is 28 days. While dose delays (within the allowed window determined below for nivolumab and daratumumab) or interruptions are permitted, the start of each cycle cannot be delayed and is fixed (ie, anchored) relative to Cycle 1 Day 1. Adjustments to the Cycle 1 Day 1 anchored schedule should not be performed. Should the start of a cycle be delayed, it is expected the following cycle begin as anchored to Cycle 1 Day 1. Delayed doses which fall outside of the allowed window for delay for the respective cycle should be skipped. Subjects may continue on study therapy even if components of the study therapy must be discontinued.

Please consult the BMS Medical Monitor or any questions regarding dose interruption or study therapy discontinuation.

4.1.5.1 Nivolumab

Cohort A

During Cycles 1 through 6, subjects may be dosed no less than 12 days from the previous dose. Nivolumab can be delayed within a 3-day window of Day 1 and Day 15 as long as the 12-day interval between 2 nivolumab 240 mg doses is respected. Doses that fall outside the allowed window should be skipped.

The first dose in Cycle 7 (Day 1) may be dosed no less than 12 days from the previous dose and for subsequent doses it should be dosed no less than 21 days from the previous dose. From Cycle 7 and beyond, nivolumab can be delayed within a 7-day window of Day 1 as long as the 12-day and 21-day intervals for the first 480 mg dose and subsequent 480 mg doses, respectively, between 2 nivolumab doses is respected. Doses that fall outside the allowed window should be skipped.

Cohort B

Cycle 1 dose (C1D15) can be delayed within a 3 day window from Day 15. Doses that fall outside the allowed window should be skipped.

From Cycle 2 (C2D1) and beyond, nivolumab can be delayed within a 7 day window from Day 1, as long as the 21-day interval between two 480 mg nivolumab doses is respected, and a 12-day interval between C1D15 and C2D1 is respected. . Doses that fall outside the allowed window should be skipped.

Nivolumab Dose Delays Due to AEs

Nivolumab administration should be delayed for the following:

- Grade 2 non-skin, drug-related AE, with the exception of fatigue
- Grade 2 drug-related creatinine, AST, ALT and/or Total Bilirubin abnormalities
- Grade 3 skin, drug-related AE
- Grade 3 drug-related laboratory abnormality, with the following exceptions:
 - Grade 3 lymphopenia or asymptomatic amylase or lipase does not require dose delay

- Grade ≥ 3 AST, ALT, Total Bilirubin will require dose discontinuation
- Any adverse event, laboratory abnormality, or intercurrent illness which, in the judgment of the investigator, warrants delaying the dose of study medication.

Participants who require delay of nivolumab should be re-evaluated weekly or more frequently if clinically indicated and resume nivolumab dosing when re-treatment criteria are met.

Criteria to Resume Treatment with Nivolumab

In order to initiate a new infusion of nivolumab the following criteria must be met:

- Platelet count $\geq 25 \times 10^9/L$ (platelet transfusion support is allowed)
- ANC $\geq 0.50 \times 10^9/L$ (growth factor support is strongly recommended if ANC $< 1.0 \times 10^9/L$)

Subjects may resume treatment with nivolumab when the drug-related AE(s) resolve(s) to Grade ≤ 1 or baseline, with the following exceptions:

- Subjects may resume treatment in the presence of Grade 2 fatigue
- Subjects who have not experienced a Grade 3 drug-related skin AE may resume treatment in the presence of Grade 2 skin toxicity
- Subjects with baseline Grade 1 AST/ALT or total bilirubin who require dose delays/interruptions for reasons other than a 2-grade shift in AST/ALT or total bilirubin may resume treatment in the presence of Grade 2 AST/ALT OR total bilirubin
- Subjects with combined Grade 2 AST/ALT AND total bilirubin values meeting discontinuation parameters should have treatment permanently discontinued
- Drug-related pulmonary toxicity, diarrhea, colitis, uveitis or neurologic toxicity must have resolved to baseline before treatment is resumed. Subjects with persistent Grade 1 pneumonitis after completion of a steroid taper over at least 1 month may be eligible for retreatment if discussed with and approved by the BMS Medical Monitor.
- Drug-related endocrinopathies adequately controlled with only physiologic hormone replacement may resume treatment after consultation with the BMS Medical Monitor.

Dose delay/interruption of nivolumab which results in treatment interruption of > 8 weeks require treatment discontinuation, with exceptions as noted below.

Nivolumab Dose Discontinuation Due to Adverse Events

Nivolumab treatment should be permanently discontinued for the following reasons:

- Any Grade 2 drug-related uveitis, eye pain or blurred vision that does not respond to topical therapy and does not improve to Grade 1 severity within the re-treatment period OR requires systemic treatment

- Any Grade 3 non-skin, drug-related AE lasting > 7 days, with the following exceptions for laboratory abnormalities, drug-related uveitis, pneumonitis, bronchospasm, hypersensitivity reactions, infusion reactions, and endocrinopathies:
 - Grade 3 drug-related uveitis, pneumonitis, bronchospasm, neurologic toxicity, myocarditis, hypersensitivity reaction, or infusion reaction of any duration requires discontinuation
 - Grade 3 drug-related endocrinopathies adequately controlled with only physiologic hormone replacement do not require discontinuation. Adrenal insufficiency requires discontinuation regardless of control with hormone replacement
 - Grade 3 drug-related laboratory abnormalities do not require treatment discontinuation except:
 - ◆ Grade 3 drug-related thrombocytopenia > 7 days or associated with bleeding requires discontinuation
 - ◆ Grade ≥ 3 drug-related AST, ALT or Total Bilirubin requires discontinuation*
 - ◆ Concurrent AST or ALT > 3 x ULN and total bilirubin > 2x ULN
- * In most cases of Grade 3 AST or ALT elevation, study treatment will be permanently discontinued. If the investigator determines a possible favorable benefit/risk ratio that warrants continuation of study treatment, a discussion between the investigator and the BMS Medical Monitor/designee must occur.
- Any Grade 4 drug-related adverse event or laboratory abnormality (including but not limited to creatinine, AST, ALT, or Total Bilirubin), except for the following events which do not require discontinuation:
 - Grade 4 neutropenia ≤ 7 days
 - Grade 4 lymphopenia or leukopenia or asymptomatic amylase or lipase
 - Isolated Grade 4 electrolyte imbalances/abnormalities that are not associated with clinical sequelae and are corrected with supplementation/appropriate management within 72 hours of their onset
 - Grade 4 drug-related endocrinopathy adverse events, such as, hyper- or hypothyroidism, or glucose intolerance, which resolve or are adequately controlled with physiologic hormone replacement (corticosteroids, thyroid hormones) or glucose-controlling agents, respectively, may not require discontinuation after discussion with and approval from the BMS Medical Monitor.
 - Any event that leads to delay in dosing lasting > 8 weeks from the previous dose requires discontinuation, with the following exceptions:
 - Dosing delays to allow for prolonged steroid tapers to manage drug-related AEs are allowed. Prior to re-initiating treatment in a subject with a dosing delay lasting > 8 weeks from the previous dose, the BMS medical monitor must be consulted. Tumor assessments should continue as per protocol even if dosing is delayed/interrupted. Periodic study visits to assess safety and laboratory studies should also continue as clinically indicated during such dosing delays/interruption.
 - Dosing delays lasting > 8 weeks from the previous dose that occur for non-drug-related reasons may be allowed if approved by the BMS medical monitor. Prior to re-initiating

treatment in a subject with a dosing delay lasting > 8 weeks, the BMS medical monitor must be consulted. Tumor assessments should continue as per protocol even if dosing is delayed/interrupted. Periodic study visits to assess safety and laboratory studies should also continue as clinically indicated during such dosing delays/interruption.

- Any AE, laboratory abnormality, or intercurrent illness which, in the judgment of the Investigator, presents a substantial clinical risk to the subject with continued nivolumab dosing.
- Immune-mediated adverse events as described in [Appendix 5](#).

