3.4 Concomitant Treatments

Subjects are permitted the use of topical, ocular, intranasal, intra-articular, and inhalational corticosteroids (with minimal systemic absorption). Immunosuppressive doses (eg, prednisone > 10 mg/day or equivalent) and/or physiologic replacement doses of systemic corticosteroids (eg, prednisone 10 mg/day) are permitted in the context of treating AEs. A brief (less than 3 weeks) course of corticosteroids for prophylaxis (eg, contrast dye allergy) or for treatment of non-autoimmune conditions (eg, delayed-type hypersensitivity reaction caused by a contact allergen) is permitted.

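### Protocol Section 4.1.5.1 gives conflicting instructions on stopping nivolumab for adrenal insufficiency: the Grade 3 block and the Grade 4 endocrinopathy exception do not agree

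*Protocol*

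**What the plan says.** Three clauses in Protocol Section 4.1.5.1 bear on the point.

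- **Discontinuation list, Grade 3 block.** It opens with a general allowance: "Grade 3 drug-related endocrinopathies adequately controlled with only physiologic hormone replacement do not require discontinuation". The next sentence of the same sub-bullet removes that allowance for one event: "Adrenal insufficiency requires discontinuation regardless of control with hormone replacement". This sentence states no grade of its own and gives the Medical Monitor no role.
- **Discontinuation list, Grade 4 block.** The exceptions to mandatory stopping include an open list of endocrine events, with thyroid disorders and glucose intolerance as the examples. The exception is limited to events "which resolve or are adequately controlled with physiologic hormone replacement (corticosteroids, thyroid hormones) or glucose-controlling agents". For those, the outcome is that they "may not require discontinuation after discussion with and approval from the BMS Medical Monitor". Adrenal insufficiency is not mentioned.
- **Criteria to resume nivolumab.** "Drug-related endocrinopathies adequately controlled with only physiologic hormone replacement may resume treatment after consultation with the BMS Medical Monitor". This has no grade limit and does not mention adrenal insufficiency.

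Two other places show how the protocol treats replacement steroids. Section 3.4 refers to "physiologic replacement doses of systemic corticosteroids (eg, prednisone 10 mg/day", so systemic corticosteroids can count as physiologic replacement. Section 3.3.2, exclusion criterion 2(j)(iv), refers expressly to steroid doses given for adrenal replacement.

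**The concern.** A site with a subject whose adrenal insufficiency is controlled on replacement corticosteroids finds one clause requiring a permanent stop and another that may allow nivolumab to continue. Nothing in the section says which takes precedence. The decision concerns permanent discontinuation for an immune-mediated toxicity that the protocol singles out, so the conflict bears on subject safety.

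There is also a smaller consequence for reporting. The SAP summarises discontinuations with their reasons (Section 7.4.2) and adverse events leading to discontinuation (Section 7.6.3). Two subjects with the same event could be counted differently because their sites followed different clauses. The section covers subjects on nivolumab in the Cohort B ND arm and Cohort A subjects still on treatment.

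**Working it through.** No plan figure is involved, so the check sets the clauses side by side for one case: drug-related adrenal insufficiency controlled on physiologic replacement corticosteroids.

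| Clause in 4.1.5.1 | Grade stated | Adrenal insufficiency named? | Outcome for this case | Medical Monitor |
|---|---|---|---|---|
| Grade 3 block, second sentence | None in the sentence; placed under Grade 3 | Yes | Permanent stop | No role given |
| Grade 4 exception | 4 | No | Stopping may not be required | Discussion and approval |
| Resumption criteria | None | No | May resume | Consultation |

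**Step 1: does the Grade 4 exception reach adrenal insufficiency?** On its wording, yes. The events listed are introduced as examples, so the list is open. Corticosteroids are given as one form of accepted replacement, and Sections 3.3.2 and 3.4 show that the protocol treats steroids as adrenal or physiologic replacement. No exclusion is written in.

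**Step 2: suppose the adrenal sentence applies to Grade 3 only.** A controlled Grade 3 case must stop. A controlled Grade 4 case may continue with approval. The more severe event then has the looser rule.

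**Step 3: suppose the adrenal sentence applies to all grades.** A controlled Grade 4 case must stop under that sentence, while the Grade 4 exception says that stopping may not be required. The two statements conflict as written, and the protocol gives no order of precedence.

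**Step 4: the resumption bullet.** The section on dose delays holds nivolumab for Grade 2 non-skin drug-related events other than fatigue, and delayed subjects resume once the re-treatment criteria are met. A controlled Grade 2 adrenal case may therefore resume after consultation under the Step 2 reading, but must stop under the Step 3 reading.

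So there is an unresolved conflict on either reading. Only its form differs.

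**The case against.** The strongest reply is that the specific sentence governs the general one. The adrenal sentence states no grade, and the Grade 4 examples are thyroid disorders and glucose intolerance. Read that way, adrenal insufficiency stops nivolumab at every grade and only a cross-reference is missing. This much stands: a reader might infer that the protocol definitely gives Grade 4 a looser rule than Grade 3, and the documents do not support that as a flat statement. It follows only if the sentence is confined to Grade 3. But the protocol states no rule that the specific overrides the general, and the sentence sits inside the Grade 3 block, so a site could fairly read it either way.

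A second reply is that the Medical Monitor is a safeguard. The Grade 4 wording is permissive and needs approval, and Section 4.1.5 sends questions about discontinuation to the Medical Monitor. This makes unsupervised continuation unlikely. It does not settle the conflict, because one clause gives the Medical Monitor discretion and the other gives none.

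Third, the resumption criteria can be read as covering only subjects whose dosing was delayed, not those who must stop permanently. That is a fair reading. A reader might count three rules in equal conflict, but the resumption bullet is secondary and does not itself mention corticosteroids. The conflict between the Grade 3 and Grade 4 clauses stands without it.

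Fourth, Appendix 5 may settle the matter. Section 3.5 requires discontinuation for severe immune-mediated events described there, and Section 4.1.5.1 lists the appendix as a further ground. Its content is not in the text available for review, so it can be shown neither to resolve the conflict nor to leave it open.

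**Conclusion.** The point holds as an internal inconsistency in current text on when nivolumab must be stopped permanently. It rests on the wording of Section 4.1.5.1 and on the assumption that Appendix 5, which could not be checked, does not already resolve it.

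Its size is small. The documents give no incidence. A reader might assume 1% to 5% among about 40 ND subjects, giving 40 × 0.01 = 0.4 to 40 × 0.05 = 2.0 expected cases, and a chance of at least one between 1 − 0.99^40 = 33% and 1 − 0.95^40 = 87%. Those rates are assumptions, and the result overstates the reach of the conflict. It counts every case, yet a Grade 3 case has a clear instruction in the discontinuation list. The Grade 3 versus Grade 4 conflict touches only controlled Grade 4 cases, with the secondary ambiguity falling mainly on Grade 2 cases after a delay.

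A reader might also infer that the main tolerability results are at risk. They are not. The primary endpoints (Protocol Section 8.3.1.1, SAP Section 4.1) count drug-related Grade 3-4 adverse events, drug-related Grade 3-4 serious adverse events and laboratory abnormalities. The ND toxicity rule (Protocol Section 3.1.1.1) counts Grade 3 or higher immune-related events and Grade 5 events. None is defined by whether nivolumab was later stopped. What can vary is the individual decision and the reported discontinuations due to adverse events. Because the decision concerns safety and the correction is cheap, it should be made.

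**What to change.** The sponsor should reconcile the Grade 3 sentence, the Grade 4 endocrinopathy exception and the resumption bullet in Section 4.1.5.1. The text should state once which grades of adrenal insufficiency the discontinuation sentence covers, and the other two clauses should refer to that statement consistently. The result should be checked against Appendix 5, since Sections 3.5 and 4.1.5.1 both rely on it. Which clinical rule governs, at any grade, is for the sponsor to decide; this review takes no position.

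The cost is one or two sentences in the protocol and a communication to sites. No procedure, sample size or analysis changes.

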4.1.5.2 Daratumumab

In Cycles 1 to 2, daratumumab doses that fall outside of the pre-specified window of +3 days must be skipped.

In Cycle 3 through 6, daratumumab dosing may be delayed for up to 1 week. If unable to administer within 1 week, then the dose should be skipped and resumption of the daratumumab continues per the protocol defined schedule.

From Cycle 7 and beyond, daratumumab can be delayed within a 21-day window. Doses that fall outside the allowed window should be skipped.

Subjects experiencing a Grade 4 (life threatening) infusion reaction related to daratumumab must permanently discontinue daratumumab.

Daratumumab Dose Delays Due to AEs

On the first day of each new treatment cycle and before each daratumumab dose, the subject will be evaluated for possible toxicities that may have occurred after the previous dose(s). Dose modifications or delays will be made based on the toxicity experienced during the previous cycle of therapy or newly encountered on Day 1 of a cycle.

Daratumumab administration should be delayed if any of the following criteria below are met, to allow for recovery from toxicity related to the study drug:

- Grade 4 hematologic toxicity except for grade 4 lymphopenia
- Grade \geq 3 thrombocytopenia
- Febrile neutropenia
- Neutropenia with infection, of any grade
- Grade \geq 3 non-hematologic toxicities with the following exceptions:
 - Grade 3 nausea or Grade 3 vomiting that responds to antiemetic treatment within 7 days
 - Grade 3 diarrhea that responds to antidiarrheal treatment within 7 days
 - Grade 3 fatigue or asthenia that was present at baseline or that lasts for < 7 days after the last administration of daratumumab

If daratumumab administration does not commence within the prespecified windows of the scheduled administration date (Table 4.1.5.2-1), that respective dose should be skipped. Administration may resume at the next planned dosing date. A missed dose will not be made up.

Table 4.1.5.2-1: Daratumumab Windows of Dosing Resumption

Cycles	Dosing Frequency	Skip dose window	Dosing Resumption
1 and 2	Weekly (QW)	> 3 days	Next planned weekly dosing date
3 to 6	Biweekly (Q2W)	> 7 days	Next planned biweekly dosing date
7 and beyond	Every 4 weeks (Q4W)	> 21 days	Next planned every 4 weeks dosing date

Criteria to Resume Treatment with Daratumumab

Administration of daratumumab may be restarted upon recovery from toxicity to Grade 2 or baseline, with the exception that Grade 2 laryngeal edema or Grade 2 bronchospasm must be fully recovered.

Any adverse event deemed to be related to daratumumab that requires a dose hold of more than 4 weeks (Cycle 1 to Cycle 6) or more than 6 weeks (Cycle 7 and beyond) will result in permanent discontinuation of daratumumab.

In order to initiate a new infusion of daratumumab the following criteria must be met:

- Platelet count $\geq 50 \times 10^9/L$ (platelet transfusion support is allowed)
- ANC $\geq 0.50 \times 10^9/L$ (growth factor support is strongly recommended if ANC $< 1.0 \times 10^9/L$).

For subjects who have experienced HBV reactivation while on study treatment, if the benefits outweigh the risks, study treatment may be resumed with concomitant antiviral prophylaxis as per local standard of care.

Daratumumab Dose Discontinuation Due to Adverse Events

Daratumumab treatment should be permanently discontinued for the following reasons:

- Grade 4 infusion reaction related to daratumumab.
- The 3rd occurrence of a Grade 3 daratumumab infusion related reaction
- Subjects experiencing ≥ 8 -week delay in all study drugs (nivolumab, daratumumab, pomalidomide, and dexamethasone) due to an AE(s) related to study treatment must be discontinued from all study treatment. Subjects experiencing delays unrelated to study therapy, for example due to radiation therapy, may delay study treatment up to 84 days. Further delays may be allowed after discussion with the BMS Medical Monitor.
- Any daratumumab related AE that requires a dose hold of > 4 weeks (Cycle 1 to Cycle 6) or > 6 weeks (Cycle 7 and beyond) will result in permanent discontinuation of daratumumab, unless, upon consultation with the sponsor and the review of safety and efficacy, continuation is agreed upon.

4.1.5.3 Pomalidomide

Pomalidomide interruption should be performed as clinically indicated at the discretion of the investigator. Subjects should be instructed that if a dose of pomalidomide has been missed and it has been less than 12 hours since the subject's regular dosing time, to take pomalidomide as soon as the subject remembers. If it has been more than 12 hours, the dose must be skipped. Subjects should not take 2 doses at the same time.

In order to initiate a new cycle of pomalidomide, the following criteria must be met:

- Platelet count $\geq 50 \times 10^9/L$
- ANC $\geq 0.50 \times 10^9/L$ (growth factor support is strongly recommended if ANC $< 1.0 \times 10^9/L$)
- Nonhematologic AEs must be resolved or improved as outlined in Section 4.1.6.

4.1.5.4 Dexamethasone

Dexamethasone interruption should be performed as clinically indicated at the discretion of the investigator. For subjects receiving daratumumab, the weekly dexamethasone that coincides with or is temporally closest to the next daratumumab dosing must be administered as part of the pre-infusion medication for daratumumab per the guidance in Section 4.1.4.2.

4.1.6 Recommended Dose Reductions for Nivolumab/Daratumumab Cohorts

The criteria presented in this section for dose modification of **dexamethasone** and **pomalidomide** are meant as general guidelines. They are based on current US standards of clinical practice. Local standards may differ and may be followed. Dose modification may occur in the setting of lower grade toxicity if the investigator, in consultation with the Medical Monitor/Sponsor, believes that it is in the interest of subject safety.

Dexamethasone

Dexamethasone dose reductions for toxicity must be performed as clinically indicated. Dose reductions and recommended management should follow the guidance in Table 4.1.6-1. Deviations to the recommended dose reductions are allowed based on the clinical judgment of the investigator.

Table 4.1.6-1: Dexamethasone Dose Reductions

CTCAE Category	Adverse Event	Treatment Adjustment
Gastrointestinal	Dyspepsia, gastric or duodenal ulcer, gastritis Grade 1 - 2 (requiring medical management)	Treat with a proton pump inhibitor. If symptoms persist despite above measures, decrease by 1 dose level.
	≥ Grade 3 (requiring hospitalization or surgery)	Hold dexamethasone until symptoms are adequately controlled. Reduce by 1 dose level and resume along with concurrent therapy with a proton pump inhibitor. If symptoms persist despite above measures, reduce to dose level -3 (dose withheld).
	Acute pancreatitis	Reduce to dose level -3 (dose withheld).
Cardiovascular	Edema ≥ Grade 3 (limiting function and unresponsive to therapy or anasarca)	Use diuretics as needed, and decrease dexamethasone by 1 dose level. If edema persists despite above measures, decrease by another dose level.
Neurology	Confusion or Mood alteration ≥ Grade 2 (interfering with function ± interfering with activities of daily living)	Hold dexamethasone until symptoms resolve. Decrease by 1 dose level and resume. If symptoms persist despite above measures, decrease by another dose level.
Musculoskeletal	Muscle weakness ≥ Grade 2 (symptomatic and interfering with function ± interfering with activities of daily living)	Hold dose until muscle weakness is ≤ Grade 1. Decrease dexamethasone by 1 dose level and resume. If weakness persists despite above measures, decrease by another dose level.
Metabolic	Hyperglycemia ≥ Grade 3 or higher	Treat with insulin or oral hypoglycemics as needed. If uncontrolled despite above measures, decrease by 1 dose level until glucose levels are satisfactory.
Constitutional	Insomnia ≥ Grade 2	Decrease by 1 dose level and resume.

Dose reduction for persistent Grade 2 or Grade ≥ 3 AEs believed to be related to dexamethasone and not listed above are permitted.

On weeks with daratumumab infusion, regardless of dexamethasone dose reduction, at least 20 mg for subjects ≤ 75 years old or at least 16 mg for subjects > 75 years old of the weekly dexamethasone dose must be administered IV as part of the premedication for daratumumab with the remainder of the weekly dexamethasone dose administered orally (PO) post-infusion. Contact the Medical Monitor to discuss dexamethasone IV premedication for subjects who reach dose level -3 and must discontinue dexamethasone due to dose limiting toxicity.

On days without daratumumab, no IV dexamethasone should be administered (Table 4.1.6-2).

Table 4.1.6-2: Dexamethasone Dose Levels

Dose Level	Reducing Dexamethasone on Weeks with Daratumumab		Reducing Dexamethasone on Weeks Without Daratumumab	
	PO	IV	PO	IV
0	≤ 75 years old - 20 mg	20 mg	≤ 75 years old - 40 mg	N/A
	> 75 years old - 4 mg	16 mg	> 75 years old - 20 mg	
-1	≤ 75 years old - 12 mg	20 mg	≤ 75 years old - 20 mg	N/A
	> 75 years old - 2 mg	16 mg	> 75 years old - 12 mg	
-2	≤ 75 years old - 0 mg	20 mg	≤ 75 years old - 12 mg	N/A
	> 75 years old - 0 mg	16 mg	> 75 years old - 8 mg	
-3	≤ 75 years old - 0 mg	Contact Medical Monitor	≤ 75 years old - 0 mg	N/A
	> 75 years old - 0 mg		> 75 years old - 0 mg	

Pomalidomide

Below are the recommended dose adjustments for the management of thrombocytopenia and neutropenia judged by the investigator to be related to pomalidomide. Information in Table 4.1.6-3 and Table 4.1.6-4 is based on pomalidomide prescribing information, which contains additional guidance on pomalidomide dosing. Investigators should follow the guidelines in the prescribing information for pomalidomide.¹⁰⁴ Some clinically relevant events and their management are presented below.

Table 4.1.6-3: Treating Thrombocytopenia Related to Pomalidomide

When Platelet Count:	Recommended Course:

 Fall to < 25,000 per mm³ Return to ≥ 50,000 per mm³ 	
 Interrupt pomalidomide treatment, follow Complete Blood Count weekly. Resume pomalidomide at 3 mg daily

 For each subsequent drop < 25,000 mm³ Return to ≥ 50,000 mm³ 	
 Interrupt pomalidomide treatment Resume pomalidomide at 1 mg less than previous dose

Table 4.1.6-4: Treating Neutropenia Related to Pomalidomide

When Neutrophil Count:	Recommended Course:

 Fall to < 500 per mm³ or febrile neutropenia (fever ≥ 38.5°C and ANC < 1,000 mm³) ANC returns to ≥ 1000 per mm³ 	
 Interrupt pomalidomide treatment, follow Complete Blood Count weekly. Resume pomalidomide at 3 mg daily

 For each subsequent drop < 500 mm³ Return to ≥ 1000 mm³ 	
 Interrupt pomalidomide treatment Resume pomalidomide at 1 mg less than previous dose

ANC, absolute neutrophil count. In case of neutropenia, consider the use of growth factors in subject management.

If necessary to co-administer strong inhibitors of CYP1A2 in the presence of strong inhibitors of CYP3A4 and P-glycoprotein, consider reducing pomalidomide dose by 50%.¹⁰⁴

